### **7.3. Study Discontinuation**

The Sponsor may terminate the study earlier than planned at any time. Investigators will be notified by the Sponsor (or designee) if the study is placed on hold, completed, or closed.

Reasons for early termination of the study may include, but are not limited to:

- Discovery of an unexpected, serious, or unacceptable risk to the subjects in the study, as recommended by the SRC (see Section 7.4 on study stopping rules).
- Decision on the part of the Sponsor to suspend or discontinue testing, evaluation, or development of the product.
- Insufficient compliance of the subjects or Investigators to protocol requirements.

The Sponsor may terminate the study earlier than planned at a specific site at any time. Reasons for early termination of the study at a specific site may include but are not limited to:

- Excessively slow recruitment.
- Poor protocol adherence.
- Inaccurate or incomplete data recording.
- Noncompliance with International Council for Harmonisation (ICH) guidelines or Good Clinical Practice (GCP).

### **7.4. Study Stopping Rules**

Any of the following will result in a temporary halt to study enrollment and dosing while the SRC evaluates results and makes recommendations:

- Any Grade 5 AE (death) except for deaths related to disease progression or clearly unrelated deaths, such as a fatal motor vehicle accident.
- Grade 4 (life-threatening) toxicity that is definitely, possibly, or probably related to ONCT-534 that is unmanageable and unexpected.
- New malignancy (distinct from recurrence/progression of previously treated malignancy) and definitely, probably, or possibly related to ONCT-534.

Safety data will be reviewed regularly by the SRC. Based on recommendations of the SRC, decisions regarding study conduct including changes to enrollment and remedial actions planned to protect subject safety will be made.

## **7.5. End of Study Definition**

The study will end when the last subject has ended study treatment (either completed the planned 108 weeks or early termination) and completed the 30-day safety follow-up (Section 8.1.12) and the study database has been locked. A clinical study report will be generated at the end of the study.

## **8. STUDY ASSESSMENTS AND PROCEDURES**

### **8.1. Clinical Assessments and Procedures**

Study assessments and procedures should be performed as indicated in the Schedule of Assessments (Section 1.3).

#### **8.1.1. Eligibility Assessments**

##### **8.1.1.1. Informed Consent**

Informed consent must be obtained before any study-related activities that are not standard of care are performed.

Informed consent is a process that is initiated prior to the individual's agreeing to participate in the study and continues throughout the individual's study participation. ICFs will be Institutional Review Board (IRB)/Ethics Committee (EC) approved and the subject will be asked to read and review the document. The Investigator will explain the research study to the subject and answer any questions that may arise and will ensure that the subject is given full and adequate oral and written information about the nature, purpose, possible risk, and benefit of the study. Subjects will have the opportunity to carefully review the written ICFs and ask questions prior to signing. The subjects should have the opportunity to discuss the study with their family or surrogates or think about it prior to agreeing to participate. The subject will sign the ICF during the Screening period prior to any procedures being done specifically for the study. Subjects must be informed that participation is voluntary and that they may withdraw from the study at any time, without prejudice. A copy of the signed ICF will be given to the subjects for their records. The informed consent process will be conducted and documented in the source document (including the date), and the ICF signed, before the subject undergoes any study-specific procedures. The rights and welfare of the subjects will be protected by emphasizing to them that the quality of their medical care will not be adversely affected if they decline to participate in this study.

##### **8.1.1.2. Eligibility and Exclusion Criteria**

Interviews, review of medical records, and eligibility testing (see Section 5.1 and 5.2) must be performed to determine if the subject is eligible to participate in the study.

##### **8.1.1.3. Demographic/Medical History**

Demographic and medical history will be collected for eligibility during Screening.

Demographic data collected should include date of birth, sex at birth, ethnicity, and race as permitted by country-specific local Health Authorities.

Medical history represents event(s) starting before informed consent and includes clinically significant diseases, surgeries, cancer history (including prior cancer therapies and procedures), and reproductive status. Further, use of alcohol or drugs of abuse, and all medications (e.g., prescription drugs, over the counter drugs, herbal or homeopathic remedies, nutritional supplements) used by the subject will be collected at the time of initial Screening visit. “Clinically significant” is defined as an event, diagnosis or presence of signs or symptoms, or laboratory value that requires either treatment, medical intervention, and/or additional monitoring or follow-up.

Prostate cancer history will include type of prostate cancer at diagnosis, original date of diagnosis, stage at diagnosis.

Prior cancer treatments (e.g., systemic therapies, surgeries, and radiation therapy) should be collected and data should include indication, start date and duration, type of therapy, best response, reason for discontinuation, and if appropriate, site of treatment. A multi-drug regimen should be recorded as one treatment regimen with the individual elements identified.

For concomitant medications at enrollment, the data collection should include the medication being taken, the start dates, dose/frequency, route of administration, and the indication.

#### **8.1.1.4. Eligibility Testing**

Results of the following must be available to determine eligibility:

- Clinical chemistry (see Section [8.1.5](#)).
- Clinical hematology and coagulation (see Section [8.1.7](#)).
- Physical examination (see Section [8.1.2](#)).
- Disease assessment to verify measurable or evaluable disease (see Section [8.2](#)).
- ECOG performance status (see [Appendix 1](#)).
- PSA level (see Section [8.1.6](#)).
- 12 lead ECG (see Section [8.1.4](#)).
- Serum testosterone level in the local laboratory.

Test results obtained within 28 days of the planned first day of ONCT-534 administration may be used.

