### 1.3. Schedule of Assessments

**Table 1: Schedule of Assessments**

Protocol Section ↓	Study Day/Week →	Screening	D0	D1	D14	D15	D28/W4	W6	W8	W12	W16	W20	W24	Q12W	W108 a	EOT a
	Visit Window (Days) →	-28 to -1			±4		±4	±4	±7	±7	±7	±7	±7	±7	±7	
8.1.1	Eligibility assessments	X														
8.1.2	Physical examination	X	X		X		X	X	X	X	X	X	X	X	X	X
8.1.3	Weight; vital signs	X	X		X		X	X	X	X	X	X	X	X	X	X
8.1.4	12-Lead Electrocardiogram	X	X		X			X		X					X	X
8.1.5	Clinical chemistry	X			X		X	X	X	X	X	X	X	X	X	X
8.1.6	Prostate-specific antigen	X					X		X	X	X	X	X	X	X	X
8.1.7	Clinical hematology; coagulation	X			X		X	X	X	X	X	X	X	X	X	X
8.1.8	Urinalysis	X					X			X			X	X	X	X
6.2.1	ONCT-534 administration in clinic		X	X	X	X	X		X	X						
8.1.9	Blood for pharmacokinetics	X	X	X b	X	X b	X		X	X						
8.1.10	Blood for biomarkers	X					X			X					X	X
8.1.11	Tumor biopsy (encouraged but optional)	X								X						
8.2	CT, chest/abdomen and pelvis c	X								X			X	X	X	
8.2	Bone scan c	X								X			X	X	X	
8.3	Adverse events	X	X	X	X	X	X	X	X	X	X	X	X	X	X d	X d
6.3	Concomitant medications	X	X	X	X	X	X	X	X	X	X	X	X	X	X	X

CT = computed tomography; D = day; EOT = End of Treatment; Q12W = every 12 weeks; W = week.

a EOT Visit at 108 weeks, or if subject discontinues prior to Week 108.

b D1 and D15 pharmacokinetic sample must be collected 24 ± 2 hours from the ONCT-534 dose on D0 and D14, respectively.

c Confirmatory scan(s) required at least 4 weeks after partial response or complete response is first documented.

d All subjects will be contacted 30 + 7 days after their last dose of ONCT-534 for a final safety interview.

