### 5.1. Subject Inclusion Criteria

1. Subject has provided informed consent and has signed an approved consent form that conforms to all applicable regulations and institutional guidelines.
2. Subject is  $\geq 18$  years of age at the time the Informed Consent Form (ICF) is signed.
3. Subject has histologically documented metastatic adenocarcinoma of the prostate confirmed by biopsy without neuroendocrine differentiation or small cell features.
4. Subject has a history of mCRPC.

5. Subject has R/R disease following treatment with at least 1 next-generation ARSI, e.g., enzalutamide, apalutamide, darolutamide, or abiraterone. Subjects with symptomatic and/or extensive visceral disease should have had prior therapy with  $\geq 1$  taxane regimen, unless considered ineligible for treatment with a taxane (per the treating Investigator) or have refused treatment with a taxane.
6. Subject has at least one measurable lesion according to Response Evaluation Criteria in Solid Tumors (RECIST) v1.1 criteria or evaluable bony disease. Lesions that have been previously irradiated will be considered measurable only if progression has been documented following completion of radiation therapy.
7. Subject has an Eastern Cooperative Oncology Group (ECOG) performance status of 0 to 2 ([Appendix 1](#)), and life expectancy of  $\geq 6$  months.
8. Subject agrees to take or continue luteinizing hormone-releasing hormone (LHRH) agonist or antagonist therapy or has undergone bilateral orchiectomy.
9. At least 2 weeks or five half-lives have elapsed, whichever is earliest, since the subject's last systemic therapy, including taxanes or other chemotherapy. At least one month has elapsed since systemic therapy with radionuclide pharmaceutical agents.
10. Subject has evidence of disease progression on or after their most recent systemic treatment, defined by any of the following criteria:
  - a. Increasing serum PSA levels as defined by the Prostate Cancer Working Group 3 (PCWG3), determined by 2 consecutive measurements (compared with a baseline or nadir value), with at least 7 days between each PSA measurement; or
  - b. Progression of measurable disease by RECIST v1.1, or progression of bony disease as defined by PCWG3 criteria.
11. Subject has a PSA level  $\geq 10$  ng/mL, or  $\geq 2$  ng/mL and  $\geq 50\%$  increase from nadir on prior therapy, whichever is lowest.
12. Subject has serum testosterone  $< 50$  ng/dL.

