**Table 2: Dose Modification of ONCT-534**

Toxicity	Treatment Modification
Grade 3 hematological toxicity	Hold treatment until recovery to Grade 1 or baseline; resume treatment at one level lower a . Transfusion and growth factors are allowed. Discontinue treatment if not resolved in 21 days.
Grade 4 or recurrent Grade 3 hematological toxicity	Hold treatment until recovery to Grade 1 or baseline; resume treatment at 2 dose levels lower a . Transfusion and growth factors are allowed. Discontinue treatment if not resolved in 21 days.
Grade 3 non-hematologic toxicity	Hold treatment until recovery to Grade 1 or baseline; resume treatment at one dose level lower a . Discontinue treatment if not resolved within 21 days.
Grade 4 non-hematologic toxicity	Permanently discontinue treatment.

a If the subject is receiving ONCT-534 at 40 mg/day, then reduce to 20 mg/day. If the subject is receiving ONCT-534 at 20 mg/day then discontinue treatment.

No dose modifications are required for the following:

- Grade 3 nausea/vomiting, anorexia, constipation, or diarrhea lasting for < 72 hours with optimal supportive care;
- Grade 3 fever lasting < 48 hours;
- Grade 3 blood urea nitrogen (BUN) or electrolyte abnormality that lasts up to 72 hours, is not considered clinically significant, and resolves spontaneously or responds to conventional medical interventions;
- Grade 3+ amylase or lipase that is not associated with symptoms or clinical manifestations of pancreatitis;
- Grade 3 fatigue, asthenia, or alopecia.

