### **8.1.2. Physical Examination**

A complete physical examination including evaluations of skin, nasal cavities, eyes, ears, lymph nodes, and respiratory, cardiovascular, gastrointestinal, neurological, and musculoskeletal systems will be performed during the Screening period. A repeat physical exam at baseline should be performed within 5 days of the first day of dosing if the Screening exam was more than 10 days prior.

A targeted physical exam will be performed at each subsequent visit as indicated in the Schedule of Assessments (Section 1.3) to assess for extra-skeletal disease evaluable on physical exam, or to evaluate any symptoms or AEs reported.

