**Table 5: Dose Escalation/De-escalation/Elimination Rule for the BOIN Design**

Actions*	The number of evaluable subjects at the current dose (cohort size n=3)											
	1	2	3	4	5	6	7	8	9	10	11	12
Escalate if # of DLT $\leq$	0	0	0	0	1	1	1	1	2	2	2	2
De-escalate if # of DLT $\geq$	1	1	2	2	2	3	3	3	4	4	4	5
Eliminate if # of DLT $\geq$	NA	NA	3	3	4	4	5	5	5	6	6	7

The steps to implement the BOIN design are described as follows:

1. All decisions to move from one dose level to another will be made by the SRC (Section 10.1.4), guided by the principles of the BOIN design.
2. Perform accelerated titration in dose cohorts 1 and 2 as follows. Treat the first subject in the cohort and escalate the dose in a one-subject-per-dose-level fashion until any of the following events is observed in the first 28 days of treatment: (i) a DLT, (ii) an existing Grade 2 condition that worsens to Grade 3; or (iii) a new Grade 2 AE. In such a case, the cohort size for the current and all subsequent cohorts will be increased to 3.
3. To assign a dose to the next cohort of subjects, the SRC will consider dose escalation/de-escalation rules presented in

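### No chemistry or hematology is scheduled between Screening and Day 14 and no baseline is defined for them, so rules that depend on pre-dose status rest on a value 1 to 28 days old

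*Combined protocol and SAP*

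**What the plan says.** - **Age of laboratory results.** Section 8.1.1.4 covers chemistry and hematology among the eligibility tests and states: "Test results obtained within 28 days of the planned first day of ONCT-534 administration may be used".
- **Schedule.** Table 1 marks clinical chemistry and clinical hematology/coagulation at Screening, leaves D0 and D1 blank, and next marks D14 (±4). Physical examination, vital signs, ECG and PK blood are all marked on D0. Section 8.1.9 places a PK sample before the first dose.
- **Unscheduled testing.** Sections 8.1.5 and 8.1.7 add only discretionary testing when there is a clinical reason.
- **Refresh rule for another assessment.** Section 8.1.2: "A repeat physical exam at baseline should be performed within 5 days of the first day of dosing", when the Screening examination is more than 10 days old. The laboratory tests have no such rule.
- **Washout.** Inclusion criterion 9 (Section 5.1): "At least 2 weeks or five half-lives have elapsed, whichever is earliest", counted from the last systemic therapy, taxanes included. It names no date by which the washout must be complete.
- **Rules that use pre-dose status.** Besides a DLT, the events that end single-subject cohorts (Section 9.5.1, step 2) are "ii) an existing Grade 2 condition that worsens to Grade 3; or (iii) a new Grade 2 AE". Table 2 says "Hold treatment until recovery to Grade 1 or baseline". Sections 8.3.1 and 8.3.3 record a laboratory change or a pre-existing condition as an AE according to whether it worsened.
- **Definition of baseline.** Section 9.5.3 defines one for PSA and Section 8.2 one for imaging. None is given for chemistry or hematology.

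**The concern.** In a first-in-human study, the last laboratory value before dosing is what separates a drug effect from what the subject brought with him. Here that value can be four weeks old. The population may be coming off chemotherapy, and Section 2.4.1 names kidney and liver among the target organs from the animal studies. A change that arose between Screening and Day 0 is first seen at Day 14 and looks treatment-emergent. Conversely, a poor old value that had since recovered can make a real drug effect look pre-existing.

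At stake are the titration trigger, the end of a treatment hold, attribution of events to ONCT-534 and the laboratory change summaries. A subject whose counts or liver or renal function no longer meet criterion 13 could also be dosed without anyone knowing. A pre-dose value that was never drawn cannot be recovered later by the investigator, the Safety Review Committee or the analyst.

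**Working it through.** The plan states no figure on this point, so there is none to reproduce. The check is day arithmetic on Table 1 and a reading of each rule that uses pre-dose status.

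**1. Table alignment.** Set against the 15 columns of Table 1, both laboratory rows fall at Screening, D14, D28/W4, W6 and every later visit. Neither falls on D0, D1 or D15.

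**2. Age of the last required value at first dose.** The Screening window is Day −28 to Day −1 and the first dose is on Day 0.
- Shortest: 0 − (−1) = 1 day.
- Longest: 0 − (−28) = 28 days.

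Section 8.1.1.4 counts from the planned first day, so a slipped start could lengthen this. Table 1 still sets Day −28 as the outer limit.

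**3. Gap to the first scheduled on-treatment value.** D14 ±4 is Day 10 to Day 18.
- Shortest: 10 − (−1) = 11 days.
- Longest: 18 − (−28) = 46 days.

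**4. Position relative to the last chemotherapy.** If a washout of w days is counted to first dose, the last chemotherapy can be on Day −w. A Day −28 laboratory value then precedes it by 28 − w days.
- w = 14 (the 2-week limb): 28 − 14 = 14 days.
- The five-half-lives limb can only shorten w. The protocol gives no half-lives, so two assumed values show the range: w = 7 gives 21 days and w = 2.5 gives 25.5 days.

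**5. Where pre-dose status enters the rules.**
- *Titration trigger.* Accelerated titration covers dose levels 1 and 2 only (Sections 9.1.1 and 9.5.1). A false trigger at level 1 takes that cohort from 1 to 3 and level 2 from 1 to 3: 2 + 2 = 4 extra subjects. At level 2 it adds 2. This error is cautious. The reverse error, a drug-related Grade 2 change read as existing, leaves the cohort at 1. Either error requires that the change qualify as an AE.
- *Table 2.* The baseline limb of the recovery rule has no defined laboratory value behind it.
- *DLT classification.* Section 8.3.7 lists nine items (1, 2, 3a–d, 4a–c). The toxicity limits are absolute grades, multiples of ULN or named clinical events, and none refers to a baseline. Pre-dose status enters by two indirect routes: the requirement that the event be attributed to ONCT-534, and item 2 (a delay of more than 14 days), because Table 2 decides when a hold ends.
- *Effect of one misattributed DLT in a cohort of 3.* 0/3 = 0 is at or below 0.236, so escalate. 1/3 = 0.333 lies between 0.236 and 0.359, so stay. Table 5 agrees. This follows from any misattributed DLT and is not specific to laboratory timing.

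**The case against.** The strongest reply is that the consequences are narrower than the gap suggests. Several stronger readings are tempting, and the documents do not support them.

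- *That DLT grading depends on an old baseline.* It does not: the Section 8.3.7 limits are absolute. Only attribution and length of hold carry any effect.
- *That a false trigger sets the size of every later cohort.* Step 2 of Section 9.5.1 refers to all subsequent cohorts, but levels 3 to 5 are outside accelerated titration. The false-trigger error is 2 to 4 extra subjects.
- *That any Grade 2 laboratory value fires the trigger.* Sections 8.3.1 and 8.3.2 exclude laboratory abnormalities without clinical significance from AEs, and Section 8.3.3 treats pre-existing conditions as medical history.
- *That the laboratory values will predate chemotherapy.* Section 5 requires the criteria to be met at Screening, exclusion 3 bars concurrent systemic therapy, and criterion 10 requires progression on or after the latest treatment. These make the sequence less likely. They do not exclude it, because Screening is a window and nothing orders the laboratory tests after the washout.
- *That ineligible subjects are in fact dosed.* This is a possibility only. Sites may test at their discretion, and Day 0 includes examination, vital signs, ECG and review of AEs and medications.

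It is also fair that 46 days joins two window extremes, that no misclassification rate can be estimated, and that escalation decisions rest with the Safety Review Committee.

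A baseline definition could be placed in the SAP that Section 9.4 defers to. That would serve the summaries, but Section 9.4 requires the SAP only before database lock, while the trigger and Table 2 operate during the study. A definition also cannot supply a value that was never drawn. The gap itself stands.

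**Conclusion.** The point holds as a design weakness that is cheap to correct. No chemistry or hematology is required between Screening and Day 14, and no baseline is defined for them. The last required value is 1 to 28 days old at first dose and 11 to 46 days before the first scheduled on-treatment value. It may also precede the last chemotherapy, by up to 14 days with a 2-week washout and longer with a shorter one. That part assumes the washout is counted to first dose, which criterion 9 leaves open.

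The direct effects are on the trigger at dose levels 1 and 2 (for changes that qualify as AEs), the Table 2 recovery rule and laboratory change summaries. The effect on DLT classification is indirect. Undetected dosing of a subject who no longer meets criterion 13 is possible. Its frequency cannot be derived from the documents.

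**What to change.** 1. In Table 1, add clinical chemistry and hematology at D0, before the first dose, taken with the existing pre-dose PK sample.
2. In Section 9, define baseline for these tests as the last value before the first dose. Apply that definition to the Section 9.5.1 trigger, Table 2, AE and DLT attribution, and laboratory summaries. The Screening value then serves if the Day 0 sample is missing.

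A Day 0 sample secures the baseline even if results return after dosing, but for that reason it would not by itself stop an ineligible subject being dosed. If the sponsor also wants the draw to confirm criterion 13, it must be taken shortly before Day 0 so that results are available before dosing.

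Cost: two extra local laboratory tubes per subject at an existing draw, the Table 1 entries and one sentence in Section 9. No extra visit is needed, and no dose, threshold or hold rule changes. A separate draw before Day 0, if chosen, may need its own attendance.

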#### **8.1.1.5. Serum Virology**

Screening virology evaluations are designed to identify subjects with active HIV, HBV, or HCV infection. HIV, HBV and /or Hep C infected subjects that have been cured or who have been on effective anti-retroviral therapy for at least one month are eligible for this trial, unless there is evidence of active infection based on the following:

- Positive HIV nucleic acid test (NAT) (> 400 copies /mL)
- Positive for HBV NAT. Subjects who are HepBSAg+, HepBCore Ab+ but NAT negative on antivirals must be discussed with the Medical Monitor.

- Positive NAT for HCV.

### **8.1.2. Physical Examination**

A complete physical examination including evaluations of skin, nasal cavities, eyes, ears, lymph nodes, and respiratory, cardiovascular, gastrointestinal, neurological, and musculoskeletal systems will be performed during the Screening period. A repeat physical exam at baseline should be performed within 5 days of the first day of dosing if the Screening exam was more than 10 days prior.

A targeted physical exam will be performed at each subsequent visit as indicated in the Schedule of Assessments (Section 1.3) to assess for extra-skeletal disease evaluable on physical exam, or to evaluate any symptoms or AEs reported.

